10.6.6 Treatment Failure (TF)

Any M3 marrow and any M2 marrow that does not qualify for PR status. A M1 marrow with evidence of circulating blasts or extramedullary disease also indicates treatment failure.

10.6.7 Relapse

Morphologic relapse after CR/CRp/CRi is defined as a reappearance of leukemic blasts in the peripheral blood or $\geq 5\%$ blasts in the bone marrow not attributable to any other cause (e.g., bone marrow regeneration after consolidation therapy). In the setting of recent treatment, if there are no circulating blasts and the bone marrow contains 5% to 20% blasts, a repeat bone marrow performed at least a week later is necessary to distinguish relapse from bone marrow regeneration. Should flow cytometric analyses suggest relapse (by the reappearance of a similar immunophenotype to the original leukemia) in the presence of $< 5\%$ blasts, or $\geq 5\%$ blasts in a regenerating marrow, a repeat bone marrow(s) performed at least a week later is necessary to confirm relapse by morphologic methods. In such instances the date of recurrence is defined as the first date that more than 5% blasts were observed in the marrow. The reappearance or development of cytologically proven extramedullary disease also indicates relapse. Molecular and/or genetic relapse is characterized by reappearance of a cytogenetics or molecular abnormality.

10.6.8 Unevaluable

Aplastic or severely hypocellular marrow with any blast percentage. In this instance, marrow evaluation should be repeated weekly until response determination can be made through at least Day 49.

10.6.9 Bone Marrow Classification:

- M1 is $< 5\%$ blasts
- M2 is 5 to 25% blasts
- M3 is $> 25\%$ blasts

10.7 Response Criteria for Patients with ALL**10.7.1 Complete Response (CR)**

Complete response (CR) is defined as an M1 marrow ($< 5\%$ blasts) with no evidence of circulating blasts or extramedullary disease and with peripheral count recovery, defined as absolute neutrophil count (ANC) $\geq 500/\mu\text{L}$ and platelet count $\geq 50,000/\mu\text{L}$ without transfusion for 7 days.

10.7.2 Complete Response with Incomplete Count Recovery (CRi)

Complete response with incomplete recovery of peripheral blood counts (CRi) is defined as an M1 marrow ($< 5\%$ blasts) with no evidence of circulating blasts or extramedullary disease and with an ANC $< 500/\mu\text{L}$ and/or platelet count $< 50,000/\mu\text{L}$.

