4.4.2 Required Observations in Cycle 1, Cohort C

All baseline studies must be performed prior to starting protocol therapy unless otherwise indicated below.

- a. Hx/Wt /Ht/BSA. Within 7 days prior to Cycle 1.
- b. Performance status. Prior to Cycle 1.
- c. Physical exam (including VS and neurologic examination). Prior to Cycle 1.
- d. CBC/diff/platelets: Prior to Cycle 1 and every week during Cycle 1. If patients have Grade 4 neutropenia then CBCs should be checked every 3 to 4 days until recovery to Grade 3 or until meeting the criteria for dose limiting toxicity.
- e. Electrolytes including Ca⁺⁺. Prior to Cycle 1.
- f. Creatinine, ALT, bilirubin. Prior to Cycle 1.
- g. Albumin. Prior to Cycle 1.
- h. Bone marrow evaluation, lumbar puncture, and evaluation of any sites of extramedullary disease. Prior to Cycle 1 and at the end of Cycle 1.
- i. Pregnancy test. Prior to Cycle 1. Female patients of childbearing potential require a negative pregnancy test prior to starting treatment; sexually active patients must use an acceptable method of birth control.
- j. Cerebral spinal fluid (CSF) cell count and differential. Within 7 days prior to Cycle 1 and at the end of Cycle 1. CSF will be obtained on Days 8, 15, and 22 only for patients who are receiving intrathecal therapy on that date.
- k. Cerebral spinal fluid (CSF) and peripheral blood pharmacokinetics. At the end of Cycle 1 at the time of the first disease evaluation for all patients with leukemia, and on Days 8, 15, and 22 for patients who are receiving intrathecal therapy. See [Section 7.3.3](#) for details.

1. Circulating tumor DNA. Prior to Cycle 1 and on Day 15 of Cycle 1. See [Section 7.3.2](#) for details.
- m. Tumor tissue submission. Prior to Cycle 1. If tissue blocks or slides are unavailable, the study chair must be notified prior to study enrollment. See [Section 7.3.1](#) for details.
- n. Patient diary. Uploaded into RAVE at the end of Cycle 1. See [Appendix VII-A](#) and [Appendix VII-B](#) for details.
- o. Neurocognitive assessments. Within 4 weeks after enrollment. See [Section 3.1.7](#) and [Appendix XI](#) for details.

This listing only includes evaluations necessary to answer the primary and secondary aims. OBTAIN OTHER STUDIES AS REQUIRED FOR GOOD CLINICAL CARE.

Comments

(Include any held doses, or dose modifications)

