10.6.3 CR with incomplete blood count recovery (CRi)

Attainment of an M1 bone marrow (< 5% blasts) with no Auer rods, no evidence of circulating blasts or extramedullary disease and with ANC $< 1000/\text{mm}^3$ or platelet count $< 100,000/\text{mm}^3$ without platelet transfusion independence (defined as: no platelet transfusions x 1 week).

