10.7.3 Partial Response (PR)

Complete disappearance of circulating blasts and achievement of M2 marrow status if M3 originally, without new sites of extramedullary disease, and with

recovery of absolute neutrophil count (ANC $\geq 500/\mu\text{L}$). Complete response in the marrow without resolution of extramedullary sites is a PR.

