10.7.4 Stable Disease (SD)

Patient does not satisfy the criteria for PD, or has recovery of ANC $\geq 500/\mu\text{L}$ and fails to qualify for CR, CRI, or PR.

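### Section 10.7 places an ALL marrow remission with ANC ≥500/µL and platelets ≥50,000/µL after a transfusion within 7 days in stable disease, so a remission rate counting CR plus CRi can be understated

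*Combined protocol and SAP*

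**What the plan says.** All four definitions stand in Section 10.7 (response criteria for ALL).

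- **CR (10.7.1):** M1 marrow, below 5% blasts, "with no evidence of circulating blasts or extramedullary disease and with peripheral count recovery", the latter meaning ANC ≥500/µL and platelets ≥50,000/µL "without transfusion for 7 days".
- **CRi (10.7.2):** M1 marrow "with no evidence of circulating blasts or extramedullary disease and with an ANC" below 500/µL and/or platelets below 50,000/µL. Transfusion is not mentioned.
- **PR (10.7.3):** an M2 marrow in a patient who began at M3, with circulating blasts cleared, ANC recovered and no new extramedullary sites. The only route for an M1 marrow is this one: "Complete response in the marrow without resolution of extramedullary sites is a PR".
- **SD (10.7.4):** among others, a patient whose ANC has recovered to ≥500/µL "and fails to qualify for CR, CRI, or PR".

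Aim 1.3.3 is the remission induction rate in relapsed or refractory leukemia. No section states whether it counts CR alone or CR plus CRi, or at which evaluation it is read. Section 9.3 defines a responder as a best response of PR or CR, does not name CRi, and points to Section 10.3.4, which belongs to the solid-tumor criteria.

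**The concern.** CRi exists to hold remission marrows that miss CR on blood counts. Here CR can be missed in three ways (ANC, platelet count, recent transfusion), but CRi lists only the first two. A patient who misses CR on transfusion alone has no remission category. The resulting order is perverse, because a lower platelet count or a lower ANC gives the better category.

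The record can occur. Section 3.2.6.1c admits leukemia patients at platelets of 20,000/mm³ and allows platelet transfusion. Section 4.4.2 schedules the response marrow together with a lumbar puncture: "Bone marrow evaluation, lumbar puncture, and evaluation of any sites of extramedullary disease. Prior to Cycle 1 and at the end of Cycle 1". At stake are the remission induction rate, if CRi counts towards it, and a response table that would list a marrow remission as stable disease. The primary analysis in Cohort A is not touched.

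**Working it through.** The plan gives no target or expected value for the remission induction rate, so there is no figure of its own to reproduce. The check is an enumeration of the definitions, followed by simple arithmetic.

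**Step 1. Classify every count pattern.** Hold fixed an M1 marrow, no circulating blasts and no extramedullary disease. Vary ANC (cut at 500/µL, Sections 10.7.1 and 10.7.2), platelets (cut at 50,000/µL, same sections) and transfusion within 7 days (Section 10.7.1, read as platelet transfusion).

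| ANC/µL | Platelets/µL | Transfused within 7 days | Category |
|---|---|---|---|
| <500 | <50,000 | no | CRi |
| <500 | <50,000 | yes | CRi |
| <500 | ≥50,000 | no | CRi |
| <500 | ≥50,000 | yes | CRi |
| ≥500 | <50,000 | no | CRi |
| ≥500 | <50,000 | yes | CRi |
| ≥500 | ≥50,000 | no | CR |
| ≥500 | ≥50,000 | yes | neither CR nor CRi |

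Of 8 patterns, 1 is CR, 6 are CRi and 1 is neither.

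**Step 2. Follow the uncovered pattern.** Take ANC 800/µL and platelets 65,000/µL two days after a transfusion.

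- CR fails on the transfusion clause.
- CRi fails because neither count is below its cut.
- PR fails because the marrow is not M2 and no extramedullary disease remains.
- PD (10.7.5) is not met.
- SD under 10.7.4 applies: ANC is ≥500/µL and CR, CRi and PR have all failed.

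Change only the platelets to 45,000/µL, or only the ANC to 400/µL, and the patient is CRi.

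**Step 3. Effect on a rate.** Let n be the number of ALL patients analysed and g the number whose final category is the uncovered pattern.

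- Rate counting CR + CRi: lowered by g/n.
- Rate counting CR only: unchanged, since these patients would be CRi, not CR.

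The documents give neither g nor n. For g = 1 and assumed n of 4, 9 or 21, the drop is 1/4 = 25.0, 1/9 = 11.1 or 1/21 = 4.8 percentage points. The sizes 9 and 21 are those of the two-stage design, which Section 9.1 extends to a secondary stratum only if nine response-evaluable patients of one histology enroll. For g = 0 the drop is zero.

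**Step 4. Can the category be repaired later?** Section 7.1 schedules leukemia evaluations after Cycles 1, 2, 4 and 6, and Section 9.4 allows 6 cycles for best response. A patient still in marrow remission at a later evaluation, 7 days free of transfusion and with adequate counts, becomes CR. The loss is final if the pattern persists, if the rate is fixed at the end of Cycle 1, or if the patient leaves protocol therapy first. Section 4.4.3 foresees early departure for consolidation such as transplant, and Section 8.1 lets the physician stop protocol therapy in the patient's interest.

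**The case against.** The strongest reply is that the intent is clear. Section 10.7.1 makes freedom from transfusion part of count recovery, and the title of Section 10.7.2 is about incomplete recovery, so a sensible reader would call this patient CRi. Section 10.7.4 also cannot be read strictly, since its opening alternative would take in every patient without PD, CR patients included. Both observations are fair. They show what was meant, but they do not override an explicit numeric rule for CRi, and a program written from the text would assign SD. The AML section writes transfusion status into its own CRi, "without platelet transfusion independence (defined as: no platelet transfusions x 1 week", so its absence from the ALL version looks like an omission.

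Three stronger readings are tempting, and the documents support none of them.

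- *The remission induction rate is understated.* This needs CRi in the numerator, which no section states, and a category that is never upgraded.
- *A recently transfused count is routine at the response visit.* The marrow and lumbar puncture are paired, but no section sets a platelet level for the puncture or calls for transfusion before it. The figure of 20,000 is an entry criterion.
- *AML would call the same patient CR.* CR in Section 10.6.1 has no transfusion clause, but it requires ANC ≥1,000/mm³ as well as platelets ≥100,000/mm³. The example in the working, with ANC 800, would be CRi there.

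It is also true that SD does not stop ALL treatment, that Cohort C is exploratory and reported descriptively, and that Section 2.7.1 reports accrual complete without saying whether any ALL patient enrolled.

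**Conclusion.** The gap is real and follows from the text alone: 1 of the 8 count and transfusion patterns in a remission marrow has no remission category and is filed as SD. The consequence is conditional. A CR + CRi rate can be understated by 1/n for each affected patient who is not later upgraded. A CR-only rate is unaffected, although the response table would still show a marrow remission as stable disease. Section 9.3 does not settle which rate is meant: it points to the solid-tumor definition, and Section 10.6.5 excludes AML PR from the response calculation.

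The size is unknown and may be zero. The percentage-point figures rest on assumed cohort sizes. The conclusion takes the CRi cuts as written and reads the transfusion clause as platelet transfusion. This is worth correcting because the defect is certain and the repair cheap, but it bears only on an exploratory, descriptive endpoint.

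**What to change.** 1. Reword Section 10.7.2 so that CRi is an M1 marrow, without circulating blasts or extramedullary disease, that does not meet the count-recovery criteria of Section 10.7.1: ANC below 500/µL, or platelets below 50,000/µL, or a platelet transfusion in the preceding 7 days. All 8 patterns are then CR or CRi, against 7 of 8 now.
2. State under aim 1.3.3 or in Section 9.3 whether the remission induction rate counts CR or CR + CRi, and whether it is read at the end of Cycle 1 or as best response within 6 cycles.
3. Classify any Cohort C ALL responses under the reworded definition.

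The cost is two short text changes. The only data needed are the transfusion dates that Section 10.7.1 already requires to assign CR. The small downside is timing: accrual is complete, and the change can only raise a CR + CRi rate or leave it unchanged. It should therefore be disclosed as a post-accrual clarification, with the number of patients whose category moves, even if that number is zero.

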10.7.3 Partial Response (PR)

Complete disappearance of circulating blasts and achievement of M2 marrow status if M3 originally, without new sites of extramedullary disease, and with

recovery of absolute neutrophil count (ANC $\geq 500/\mu\text{L}$). Complete response in the marrow without resolution of extramedullary sites is a PR.

10.7.4 Stable Disease (SD)

Patient does not satisfy the criteria for PD, or has recovery of ANC $\geq 500/\mu\text{L}$ and fails to qualify for CR, CRI, or PR.

10.7.5 Progressive Disease (PD)

An increase of at least 25% in the absolute number of bone marrow leukemic cells, development of new sites of extramedullary disease, or other laboratory or clinical evidence of PD, with or without recovery of ANC or platelets.

10.7.6 MRD Negative

Patients will be considered MRD negative if their bone marrow has less than 0.01% blasts by flow cytometric evaluation. MRD should be performed by a COG approved laboratory.

10.8 CNS Leukemia at Diagnosis for Patients with ALL

| | |
|---------|--|
| CNS 1: | In cerebral spinal fluid (CSF), absence of blasts on cytopspin preparation, regardless of the number of WBCs. |
| CNS 2: | In CSF, presence $< 5/\mu\text{L}$ WBCs and cytopspin positive for blasts, or $\geq 5/\mu\text{L}$ WBCs but negative by Steinherz/Bleyer algorithm: |
| CNS 2a: | $< 10/\mu\text{L}$ RBCs; $< 5/\mu\text{L}$ WBCs and cytopspin positive for blasts; |
| CNS 2b: | $\geq 10/\mu\text{L}$ RBCs; $< 5/\mu\text{L}$ WBCs and cytopspin positive for blasts; |
| CNS 2c: | $\geq 10/\mu\text{L}$ RBCs; $\geq 5/\mu\text{L}$ WBCs and cytopspin positive for blasts but negative by Steinherz/Bleyer algorithm (see below). |
| CNS 3: | In CSF, presence of $\geq 5/\mu\text{L}$ WBCs and cytopspin positive for blasts and/or clinical signs of CNS leukemia: |
| CNS 3a: | $< 10/\mu\text{L}$ RBCs; $\geq 5/\mu\text{L}$ WBCs and cytopspin positive for blasts; |
| CNS 3b: | $\geq 10/\mu\text{L}$ RBCs, $\geq 5/\mu\text{L}$ WBCs and positive by Steinherz/Bleyer algorithm (see below); |
| CNS 3c: | Clinical signs of CNS leukemia (such as facial nerve palsy, brain/eye involvement or hypothalamic syndrome). |

Method of Evaluating Initial Traumatic Lumbar Punctures:

If the patient has leukemic cells in the peripheral blood and the lumbar puncture is traumatic and contains $\geq 5 \text{ WBC}/\mu\text{L}$ and blasts, the following algorithm should be used to distinguish between CNS 2 and CNS 3 disease:

$$\frac{\text{CSF WBC}}{\text{CSF RBC}} > 2X \frac{\text{Blood WBC}}{\text{Blood RBC}}$$

A patient with CSF WBC $\geq 5/\mu\text{L}$ blasts, whose CSF WBC/RBC is 2X greater than the blood WBC/RBC ratio, has CNS disease at diagnosis.

Example: CSF WBC = $60/\mu\text{L}$; CSF RBC = $1500/\mu\text{L}$; blood WBC = $46000/\mu\text{L}$; blood RBC = $3.0 \times 10^6/\mu\text{L}$:

$$\frac{60}{1,500} = 0.04 > 2X \frac{46,000}{3.0 \times 10^6} = 0.015$$

10.9 CNS Leukemia at Diagnosis for Patients with AML

| | |
|----------|---|
| Negative | In cerebral spinal fluid (CSF), absence of blasts on cytopspin preparation, regardless of the number of WBCs. |
| Positive | In CSF, presence blasts on cytopspin, regardless of the number of WBCs. |

11.0 ADVERSE EVENT REPORTING REQUIREMENTS

11.1 Purpose

Adverse event (AE) data collection and reporting, which are required as part of every clinical trial, are done to ensure the safety of patients enrolled in the studies as well as those who will enroll in future studies using similar agents. Certain adverse events must be reported in an expedited manner to allow for timelier monitoring of patient safety and care. The following sections provide information about expedited reporting.

11.2 Expedited Reporting Requirements – Serious Adverse Events (SAEs)

To ensure compliance with these regulations/this guidance, AEs must be submitted according to the timeframes in the AE reporting table assigned to the protocol, using the CTEP Adverse Event Reporting System (CTEP-AERS).

Any AE that is serious qualifies for expedited reporting. An AE is defined as any untoward medical occurrence associated with the use of a drug in humans, whether or not considered drug related. A Serious Adverse Event (SAE) is any adverse drug event (experience) occurring at any dose that results in ANY of the following outcomes:

- 1) Death.
- 2) A life-threatening adverse drug experience.
- 3) An adverse event resulting in inpatient hospitalization or prolongation of existing hospitalization (for ≥ 24 hours). This does not include hospitalizations that are part of routine medical practice.
- 4) A persistent or significant incapacity or substantial disruption of the ability to conduct normal life functions.
- 5) A congenital anomaly/birth defect.
- 6) Important Medical Events (IME) that may not result in death, be life threatening, or require hospitalization may be considered a serious adverse drug experience when, based upon medical judgment, they may jeopardize the patient or subject and may require medical or surgical intervention to prevent one of the outcomes listed in this definition.

11.3 Specific Examples for Expedited Reporting

11.3.1 SAEs Occurring More than 30 Days After Last Dose of Study Drug

Any Serious Adverse Event that occurs more than 30 days after the last administration of the investigational agent/intervention **and** has an attribution of a

possible, probable, or definite relationship to the study therapy must be reported according to the CTEP-AERS reporting table in this protocol.

11.3.2 Persistent or Significant Disabilities/Incapacities

Any AE that results in persistent or significant incapacity or substantial disruption of the ability to conduct normal life functions (formerly referred to as disabilities), congenital anomalies or birth defects, must be reported via CTEP-AERS if it occurs at any time following treatment since these are considered serious AEs.

11.3.3 Death

Reportable Categories of Death

- Death attributable to a CTCAE term.
- Death Neonatal: Newborn death occurring during the first 28 days after birth.
- Sudden Death NOS: A sudden (defined as instant or within one hour of the onset of symptoms) or an unobserved cessation of life that cannot be attributed to a CTCAE term associated with Grade 5.
- Death NOS: A cessation of life that cannot be attributed to a CTCAE term associated with Grade 5.
- Death due to progressive disease should be reported as ***Grade 5 “Disease progression”*** under the system organ class (SOC) of “General disorder and administration site conditions”. Evidence that the death was a manifestation of underlying disease (e.g., radiological changes suggesting tumor growth or progression: clinical deterioration associated with a disease process) should be submitted.

Any death occurring ***within 30 days*** of the last dose, regardless of attribution to the investigational agent/intervention requires expedited reporting within 24 hours.

Any death occurring ***greater than 30 days*** after the last dose of the investigational agent/intervention requires expedited reporting within 24 hours ***only if*** it is possibly, probably, or definitely related to the investigational agent/intervention.

11.3.4 Secondary Malignancy

A ***secondary malignancy*** is a cancer caused by treatment for a previous malignancy (e.g., treatment with investigational agent/intervention, radiation or chemotherapy). A metastasis of the initial neoplasm is not considered a secondary malignancy.

All secondary malignancies that occur following treatment with an agent must be reported via CTEP-AERS. Three options are available to describe the event:

- Leukemia secondary to oncology chemotherapy
- Myelodysplastic syndrome
- Treatment related secondary malignancy

Any malignancy possibly related to cancer treatment (including AML/MDS) must also be reported via the routine reporting mechanisms outlined in this protocol.

11.3.5 Second Malignancy

A ***second malignancy*** is one unrelated to the treatment of a prior malignancy (and is **NOT** a metastasis from the initial malignancy). Second malignancies require **ONLY** routine reporting via CDUS unless otherwise specified.

11.3.6 Pregnancy, Pregnancy Loss, and Death Neonatal

NOTE: When submitting CTEP-AERS reports for “Pregnancy”, “Pregnancy loss”, or “Neonatal loss”, the Pregnancy Information Form, available at:

http://ctep.cancer.gov/protocolDevelopment/electronic_applications/docs/PregnancyReportForm.pdf, needs to be completed and faxed along with any additional medical information to [contact]. The potential risk of exposure of the fetus to the investigational agent(s) or chemotherapy agent(s) should be documented in the “Description of Event” section of the CTEP-AERS report.

11.3.6.1 **Pregnancy**

Patients who become pregnant on study risk intrauterine exposure of the fetus to agents that may be teratogenic. For this reason, pregnancy occurring on study or within 6 months following the last dose of study therapy should be reported in an expedited manner via CTEP-AERS as **Grade 3 “Pregnancy, puerperium and perinatal conditions - Other (pregnancy)”** under the ***Pregnancy, puerperium and perinatal conditions*** SOC.

Pregnancy needs to be followed **until the outcome is known**. If the baby is born with a birth defect or anomaly, then a second CTEP-AERS report is required.

11.3.6.2 **Pregnancy Loss (Fetal Death)**

Pregnancy loss is defined in CTCAE as “*Death in utero*”. Any Pregnancy loss should be reported expeditiously as **Grade 4 “Pregnancy loss”** under the ***“Pregnancy, puerperium and perinatal conditions”*** SOC. Do NOT report a pregnancy loss as a Grade 5 event since CTEP-AERS recognizes any Grade 5 event as a patient death.

11.3.6.3 **Death Neonatal**

Neonatal death, defined in CTCAE as “*Newborn deaths occurring during the first 28 days after birth*” that is felt by the investigator to be at least possibly due to the investigational agent/intervention, should be reported expeditiously.

A neonatal death should be reported expeditiously as Grade 4 “*Death neonatal*” under the ***“General disorders and administration”*** SOC **when the death is the result of a patient pregnancy or pregnancy in partners of men on study**.

Do NOT report a neonatal death resulting from a patient pregnancy or pregnancy in partners of men on study as a Grade 5 event since CTEP-

AERS recognizes any Grade 5 event as a patient death.

